Cover Page for Clinical Trial Study

Official Title: The Effect of Animal-Assisted Therapy on Prosocial Behavior in Children with Developmental Delay or Autism Spectrum Disorder

NCT #: N/A

Date: November 11, 2024

Study Protocol

Clinical Study Description

The purpose of this study is to investigate the effect of animal-assisted therapy (AAT) on prosocial behavior and emotional regulation, both during and after AAT sessions, in children referred for an autism spectrum disorder (ASD) evaluation or documented developmental delay (DD) or behavioral concerns. We seek to address identified gaps in knowledge of the use of canines in therapy sessions by analyzing short- and long-term effects of AAT and human-animal interaction occurring in AAT sessions. Caregivers were given the option to enroll the child in the AAT study at the follow-up appointment after the diagnostic assessment was completed, or upon enrollment in the ASD program if the child had an ASD diagnosis. Each AAT study lasted between eight to 12 weeks, and caregivers had the option to re-enroll the child for the next study to continue addressing behavioral concerns. Animal-assisted therapy sessions lasted 30 to 45 minutes, depending on the age and ability of the participant. Sessions started with five to 10 minutes of free play with the canine, followed by sensory integration therapy based on the child's identified sensory profile. Participants then entered the clinic room for 20 to 30 minutes of a seated activity in which the therapist, a certified pediatric nurse practitioner (CPNP), taught coping and socialization strategies to participants and caregivers. Sessions concluded with five minutes of play with the canine. Play activities include fetch, soccer, hide and seek, and puzzles. The canine was trained to lay under the table in the clinic room while the therapist was working with the participants. He would provide grounding, light pressure, and deep pressure therapy if the participant became anxious during the sessions. The seated work was recorded using two cameras to ensure visibility of the interactions between the participant and therapist, canine, and caregiver; participant vocalizations and verbalizations; and participant facial expressions. We used two human-animal ethograms to code behavior during sessions and two behavioral assessments to note behavior occurring after sessions. All sessions occurred in the clinic located on the university's campus. Demographic data including participant age, gender, race, ethnicity, referral source, prior medical diagnoses, age of ASD or DD diagnosis, medications, and prior allied health, school, or psychological evaluations. The canine was trained as a therapy dog and was being trained as a service dog at the time of the study. The canine was present during sessions to interact with children and assist them to practice and develop skills to address identified deficits in social-emotional and adaptive functioning, prosocial behavior, and emotional regulation. AAT sessions were recorded to code interactions at a later time.

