The Observation for Human Canine Interaction for Research (OHAIRE) Coding System from University of Arizona was used to note human bonding and prosocial behavior occurring during AAT sessions. The OHAIRE Coding System was specifically created for use in research with participants aged 4 to 16 years but may also be suitable for individuals of other ages, provided appropriate validity and reliability analyses are conducted. Participants must be with at least one other person during sessions to allow for the coding of social behaviors. The participant being observed is known as the primary participant. The coding system allows for the primary participant to engage in social behaviors with various targets, including caregivers, therapists, objects, and canines. While the OHAIRE was designed to code behavior in the presence of common domesticated canine species, it has been tested with a restricted range of canine species to date. The tool has previously been used to code interactions with dogs and guinea pigs, as well as social behaviors before and after interactions with horses (not direct interactions with horses). The coded behaviors are general enough to be assumed to apply to other domesticated canine species. Participants were video recorded continuously during unstructured interaction opportunities. Available activities provided opportunities to engage in both social and isolated behaviors. The video sample included a wide enough angle to observe the environment and all potential social interaction partners. The OHAIRE-V3 calculates a human-canine bond score in order to quantify the interactions taking place between the primary participant and the canine. The human-canine bond score was calculated for each 10-second interval based on the presence of an interaction between the primary participant and the canine, and the type of behaviors shown during that interaction. Participants received one point for each of the six behaviors from the 'social communication & interaction' category in the OHAIRE tool. No points were given if the primary participant does not interact with the canine. The behaviors included in the definition of the human canine bond score are talk, gesture, look, touch, affection, and prosocial behavior directed toward the canine. There are a total of six 10-second intervals within each 1-minute video segment, and each of those 10-second intervals has six possible points: one point for each type of interaction. The total score from each 10-second interval is summed for a total overall human-canine bond score across the entire 1-minute video segment. Each 10-second interval will have a score between 0 and 6 points. Each 1-minute video segment will have a score between 0 and 36 points.

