Lastly, the Positive and Negative Affect Schedule (PANAS) was administered weekly to measure therapeutic effects occurring in everyday life outside of the AAT session. The PANAS is a 20-item questionnaire utilizing a 5-point Likert scale to assess positive and negative affect occurring the week prior to administration. Each domain has 10 items with scores ranging from 10 to 50, with lower scores reflecting lower levels of positive or negative affect and higher scores signifying higher positive or negative affect²⁹. Total scores on each scale are obtained by adding the scores for each item. Analysis of the PANAS demonstrates very good internal consistency reliability, with alphas ranging from 0.86 to 0.90 for Positive affect and from 0.84 to 0.87 for Negative affect.

Statistical Analysis Plan

This present study used standardized instruments to investigate human-animal interaction (HAI) occurring during AAT sessions and prosocial behavior and emotional regulation demonstrated by participants outside of AAT sessions. SPSS and Microsoft Excel were used to run the analysis. Descriptive statistics were utilized to compare prosocial behavior and emotional regulation occurring apart from AAT sessions between the two groups based on the self-report questionnaires completed by caregivers. A total of 144 sessions were conducted, 84 of which were recorded and coded to analyze HAI during sessions. Independent t-tests were used to analyze the differences in human-animal interaction among children with ASD with varying verbal abilities from the recorded sessions. The homogeneity of the variance (HOV) assumption between two groups was checked using Levene's test for equality of variances in SPSS program before conducting the t-tests analysis. Results of t-tests with adjusted degrees of freedom value were reported if the HOV was violated. The null hypothesis was set to reflect no significant difference in HAI between verbal and nonverbal groups for the independent t-tests; therefore, a significant difference in the human-animal interaction behaviors regarding the children's verbal abilities could be confirmed if the t-test results reject the null hypothesis. Cohen's d was used to report the effect sizes of the independent t-tests; values up to 0.20 were interpreted as small, 0.50 as medium, and 0.80 as large effect size.

Protocol Number: 2201382953
Investigator: [name]

Expiration Date: 03/31/2024
Last Approval Date: 04/01/2023

University of Arkansas System

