Title: The Effect of Animal-Assisted Therapy on Prosocial Behavior in Children with Developmental Delay or Autism Spectrum Disorder

- **What is the purpose of this research? Please explain both why you are doing the research (class assignment, thesis, etc.) AND/OR state your hypothesis. See attachment is not a sufficient response.**

The proposed project will investigate the effects of utilizing animal-assisted therapy (AAT) in the therapy plan for youth with autism spectrum disorder (ASD) or developmental delay (DD). The purpose of this study is to explore identified gaps in knowledge pertaining to AAT in pediatric ASD and DD care management. Specifically, we seek to document canine care and behavior during training and AAT sessions, assess human and canine interaction during AAT sessions, and analyze long-term effects of AAT on social-emotional and adaptive functioning in the pediatric participants once the sessions have ended. This study will address the following research questions: 1. What measures should be taken to ensure protection of the canine before, during, and after AAT sessions as well as during training? 2. What human-animal interaction behaviors are present during AAT sessions with pediatric participants ages 12 months to 18 years? 3. What effect does AAT have on pediatric development and social-emotional and adaptive functioning? 4. Are effects in development and social-emotional and adaptive functioning produced by AAT sustainable after completion of the 12-week AAT program?

- **Are you collecting data about living individuals?**

Yes

- **Are you collecting data through intervention or interaction with these individuals?**

Yes

- **Beyond the basic Participant Types (children, UofA Students, adults, etc.) named elsewhere in this application, do you have a target population (particular group of people) you want to recruit? Some examples might be students in a particular class, members of a particular group or network, people in a specific age range (whether adult or minor), children in a particular school or class, etc.**

Yes

- **Describe your target population.**

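### Verbal and nonverbal children are compared by t-tests without age, over a very wide planned age range, so an age difference between the groups can appear as a verbal-ability difference

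*Combined protocol and SAP*

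**What the plan says.** The Statistical Analysis Plan, repeating the Design section, states: "Independent t-tests were used to analyze the differences in human-animal interaction among children with ASD with varying verbal abilities from the recorded sessions". The groups are defined by a characteristic of the child: "The null hypothesis was set to reflect no significant difference in HAI between verbal and nonverbal groups for the independent t-tests". The one refinement concerns variances, through Levene's test: "Results of t-tests with adjusted degrees of freedom value were reported if the HOV was violated". The caregiver questionnaires are handled more simply still: "Descriptive statistics were utilized to compare prosocial behavior and emotional regulation occurring apart from AAT sessions between the two groups". No covariate, stratification, matching, age restriction or check of age balance is described.

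On age, the research questions in the Human Subjects Protocol Interview refer to "pediatric participants ages 12 months to 18 years", while the target-population answer in the same form starts at 18 months. Age is on file: the Clinical Study Description lists "Demographic data including participant age, gender, race, ethnicity, referral source, prior medical diagnoses, age of ASD or DD diagnosis", and the procedures answer says demographic data are collected on all participants.

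Two measurement details also involve age. The Clinical Study Description lets session length run from 30 to 45 minutes according to age and ability, while Methods records ethogram frequency as a plain tally. Methods also says that OHAIRE was created for "participants aged 4 to 16 years but may also be suitable for individuals of other ages, provided appropriate validity and reliability analyses are conducted".

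**The concern.** The comparison is observational, so anything that differs between verbal and nonverbal children and also affects behaviour with a dog can produce a group difference. Age is the obvious candidate. Over a range that starts at 12 or 18 months, a child may be nonverbal partly through being very young, and age plausibly affects how a child talks to, touches, plays with and cares for a dog. The documents themselves give age a second route: older or more able children may be observed for longer, and a tally grows with time observed.

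The SAP treats a rejected null hypothesis as confirming a difference that goes with verbal ability. If the groups differ in age, the same rejection could come from age alone, and nothing in the planned output would show it. Adjusted degrees of freedom deal with unequal variances and leave this bias untouched.

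**Working it through.** The documents give no power, sample-size or alpha figure, so there is no stated figure to reproduce. What follows illustrates the size of the risk.

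**Inputs from the documents.** 20 children (Subjects table, Protocol Summary); 84 coded sessions out of 144 (SAP); Cohen's d of 0.20, 0.50 and 0.80 read as small, medium and large (SAP).

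**Assumptions not in the documents.** Two-sided 5% test; 10 children per group, one value per child; linear age effect; within-group correlation r between age and outcome of 0.3 or 0.5; age gap g between groups of 0.5 or 1 within-group SD; no true verbal effect.

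For scale, ages spread evenly over 1 to 18 years have an SD of 17/√12 = 4.9 years (16.5/√12 = 4.8 from 18 months). A gap of 0.5 SD is then about 2.5 years and 1 SD about 4.9 years.

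**Step 1: spurious effect size.** With outcome SD 1 within group, the expected group difference is d = r × g.

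**Step 2: false-positive rate of the unadjusted t-test.** The statistic is noncentral t with 18 degrees of freedom and noncentrality d × √(10/2) = 2.236d, against a critical value of 2.10. The rates were also simulated with 10,000 data sets per row.

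| r | g (SD) | d = r × g | Simulated | Noncentral t |
|---|---|---|---|---|
| 0.3 | 0.5 | 0.15 | 6.2% | 6.2% |
| 0.5 | 0.5 | 0.25 | 7.9% | 8.3% |
| 0.3 | 1.0 | 0.30 | 9.2% | 9.7% |
| 0.5 | 1.0 | 0.50 | 18.4% | 18.5% |

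With no age gap the simulated rate is about 5%. The last row reaches what the SAP calls medium with no verbal effect present.

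**Step 3: age added at child level.** In the same simulations, a linear model with verbal group and age gave 4.5% to 5.2% in every 10-versus-10 setting, with an estimated group difference of 0.000 to 0.008 SD.

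**Step 4: age added at session level.** The SAP analyses recorded sessions. If the planned count of children holds, 84/20 = 4.2 sessions come from each child on average. I simulated 10 versus 10 children with 42 sessions per group, g = 1 and r = 0.3 or 0.5, and regressed session values on group and age. The false-positive rate was about 13%, 24% and 31% at assumed within-child correlations ρ of 0.2, 0.5 and 0.7. On per-child means it was about 5%.

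A rough check uses the design effect 1 + 3.2ρ = 1.64, 2.60 and 3.24. The corresponding rate 2 × [1 − Φ(1.96/√design effect)] is 13%, 22% and 28%. This is slightly low because it ignores the small number of children. Putting age into the model therefore repairs the test only if the child is the unit of analysis.

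**Step 5: observation time.** The seated, recorded part lasts 20 to 30 minutes. At the same behaviour rate, a 30-minute recording gives up to 30/20 = 1.5 times the tally of a 20-minute one. The documents tie total session length to age and ability. They do not say how far the recorded part follows, so 1.5 is an upper bound.

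**The case against.** The strongest reply is that Objective 1 asks only whether interactions differ with verbal ability. That is a question of association, and an unadjusted difference answers it. Adjusting for age changes what is estimated, and with about 20 children whose ages may barely overlap, the adjusted coefficient could rest on extrapolation. This stands in part. It is the reason to report the unadjusted difference as well, to show age by group, and to word results as associations. It does not justify leaving age out, because a reader will take a significant result as being about verbal ability.

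A second reply is that the ages analysed may be narrower than the planned range. The t-tests concern children with ASD in recorded sessions, and the data-collection list gives the SDQ for 3 to 16 years and the PANAS for 9 to 14 (Methods gives the SDQ as 2 to 18). This also stands: whether toddlers were analysed, or whether the nonverbal group is younger, cannot be read from the documents.

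A reader might also infer that no reliability work is planned for OHAIRE. That goes too far, because the Human Subjects Protocol Interview plans ELAN coding software to support inter-rater reliability. What is not described is any validity or reliability analysis specific to children outside 4 to 16. The share of such children is unknown.

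**Conclusion.** The point holds as a risk of confounding. The groups are not randomised, the tests carry no covariate, the planned age range is very wide under either lower bound, and age is collected but unused. Under the assumptions above, at child level, the spurious d is 0.15 to 0.50 and the false-positive rate about 6% to 18%. The lower end, with a 0.5 SD gap and r = 0.3, is barely above nominal.

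Two stronger readings are tempting and are not supported. One is that any difference found is in fact an age effect. The ages by verbal group are not given, so neither the size nor the direction of bias can be stated. The other is to count 42 versus 42 sessions as independent. The unadjusted rate then rises to 61% at r = 0.5 and a 1 SD gap, and age appears to restore 5%. Both figures need 84 independent sessions, which is implausible with 20 planned children, weekly sessions and re-enrolment. Clustering is a separate problem that age adjustment does not cure.

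**What to change.** 1. Report the age distribution by verbal group for the children actually analysed, and reconcile the two lower age bounds (12 and 18 months).
2. Replace each t-test with a regression of the outcome on verbal group plus age in years (continuous), on per-child means or as a mixed model with a random effect for child. A session-level regression would still treat repeated sessions as independent.
3. Report the unadjusted difference beside the adjusted one, and describe both as associations.
4. For ethogram tallies, consider counts per recorded minute, since age adjustment may not remove differences in observation time that follow ability.
5. Add a sensitivity analysis limited to ages 4 to 16 for OHAIRE outcomes.

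The cost is SAP wording and a re-analysis of data already held. The adjustment uses one degree of freedom and widens the interval if age and verbal status are strongly related. If the groups' ages barely overlap, the adjusted estimate relies on extrapolation. Item 1 would show this, and the report should then say so. About 20 children can support age as a covariate, but not a long list of covariates.

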
The 3-AAT Observation ethogram, adapted with permission from Johns Hopkins University, was used to code both canine and human interaction during AAT sessions. The revised ethogram appraises the frequency of six domains of human interaction (affection, play, care, communication, comfort, withdrawal) and 24 subdomains of human behavior that can occur in an AAT session as seen in Table 1. The ethogram assesses the frequency, intensity, and duration of the interactions between the canine and child. Frequency is measured by a tally count and duration is assessed by rounding either up or down to the nearest 30 second mark. Each interaction has a code for intensity from 0 (not intense) to 3 (the most intense), and the mode of the interaction was entered to run the analysis.

The Strengths and Difficulties Questionnaire (SDQ) is a 25-item tool developed to assess five domains: Emotional Problems, Conduct Problems, Hyperactivity, Peer Problems, and Prosocial. The SDQ is the most used instrument in measuring therapeutic effect of interventions within the emotional state in children and adolescents ages 2 to 18 years, demonstrating reliable internal consistency and validity. The SDQ has two versions, one to be administered at the initiation of therapy and then a follow-up version that includes two additional questions examining the impact of the therapeutic intervention. Scores from four behavioral domains range from zero ("normal") to 10 ("very high concerns"), while Prosocial domain scores are reversed so that 10 indicates "normal" behavior and zero signifies "very high concerns". The SDQ also assesses the total, impact, internalizing, and externalizing scores to provide a complete overview of the child's behavior during the past four weeks. Total scores are the sum of the behavior domains except the Prosocial domains and range from zero (normal) to 40 (very high). Impact scores range from zero (normal) to 10 (very high) and reflect overall distress and impairment interfering with daily social interactions. Internalizing scores reflect the Emotional Problems and Peer Problems domains, while Externalizing scores are the sum of the Conduct Problems and Hyperactivity domains. Both the Internalizing and Externalizing domain scores range from zero (normal) to 20 (very high). The initial SDQ was administered at the beginning of the study and the follow-up assessment was used subsequently every four weeks until the study concluded.

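### The t-tests on 3-AAT frequency tallies name no child-level unit, no adjustment for coded time and no allowance for skew: false differences are likely if sessions are the units, and power can be lost if child means are

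*Combined protocol and SAP*

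**What the plan says.** The Methods section describes the 3-AAT ethogram as covering six domains and 24 subdomains of human behaviour: "Frequency is measured by a tally count and duration is assessed by rounding either up or down to the nearest 30 second mark". Intensity is handled differently: "Each interaction has a code for intensity from 0 (not intense) to 3 (the most intense), and the mode of the interaction was entered". The OHAIRE bond score is a bounded sum: "Each 1-minute video segment will have a score between 0 and 36 points".

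The Design section and the Statistical Analysis Plan give the same single inferential method for human-animal interaction: "Independent t-tests were used to analyze the differences in human-animal interaction among children with ASD with varying verbal abilities from the recorded sessions". The only assumption check is "The homogeneity of the variance (HOV) assumption between two groups was checked using Levene's test for equality of variances", and the only remedy is "Results of t-tests with adjusted degrees of freedom value were reported if the HOV was violated". The data are described thus: "A total of 144 sessions were conducted, 84 of which were recorded and coded to analyze HAI during sessions".

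Neither section names a child-level summary, a model for repeated sessions, a rate or offset for coded time, a transformation, a count model or a rank test. The Subjects table of the Protocol Summary lists 20 children. The number analysed, the verbal/nonverbal split and the alpha level are not given.

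**The concern.** Objective 1 asks whether interaction with the canine differs by verbal ability, and these t-tests are its only formal analysis. Three things are left open for the tallies.

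- **Unit.** Each child attended over 8 to 12 weeks and could re-enrol, so sessions come in clusters. A t-test that counts sessions as independent overstates the information.
- **Exposure.** The Clinical Study Description says session length varied from 30 to 45 minutes according to age and ability. A raw tally therefore mixes rate with time observed, and ability may be related to the grouping variable.
- **Skew.** Counts of specific behaviours may be right-skewed, with a spread that rises with the mean. A few very active children can then dominate a raw mean difference. Adjusted degrees of freedom protect the error rate but do not recover the lost efficiency.

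The first two can create a difference that is not there. The third can hide one that is.

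**Working it through.** The plan states no power, alpha or expected tally, so there is no figure to reproduce. Two-sided 5% is assumed throughout.

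**1. If sessions are the units.** Inputs: 84 coded sessions (Statistical Analysis Plan) and 20 children (Subjects table), so m = 84/20 = 4.2 sessions per child. With correlation ρ between sessions of one child, the variance of a group mean is inflated by f = 1 + (m − 1)ρ, and a nominal 5% test has actual size of about 2[1 − Φ(1.96/√f)]. ρ is not in the documents, so a range is shown:

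| ρ (assumed) | f | 1.96/√f | actual size |
|---|---|---|---|
| 0.1 | 1 + 3.2 × 0.1 = 1.32 | 1.71 | 8.8% |
| 0.5 | 1 + 3.2 × 0.5 = 2.60 | 1.22 | 22% |
| 1.0 | 1 + 3.2 × 1.0 = 4.20 | 0.96 | 34% |

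Simulation of the plan's rule (Levene at 5%, then pooled or adjusted t) agrees. With 10 v 10 children, 84 sessions, child log-SD 0.3 to 0.8 and no true difference, the session-level test rejects 10 to 37% of the time. Logging session tallies does not help (9 to 34%). Using child means restores 3 to 5%, and logged child means give 4 to 6%.

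**2. Coded time.** 45/30 = 1.5. If coded time follows session length and length differs between the verbal groups, tallies could differ by a factor of up to 1.5 with identical rates. The documents do not say whether length differed by group or how many minutes were coded.

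**3. If children are the units: validity.** With 10 independent observations per group, the plan's rule held 2.4 to 6.1% across Poisson, negative-binomial and Poisson-lognormal tallies. It becomes conservative under heavy skew.

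**4. If children are the units: power.** Assumed: 20 children, mean of 4 sessions each, Poisson tallies with gamma child rates (smaller shape means more skew), 2 v 6 per session. Each cell gives the plan's power, then that of an unequal-variance t-test on log(1 + child mean):

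| Split | shape 0.5 | shape 1 | shape 2 |
|---|---|---|---|
| 10 v 10 | 18, 27% | 44, 52% | 78, 81% |
| 14 v 6, smaller group more active | 8, 15% | 22, 36% | 49, 64% |
| 14 v 6, larger group more active | 25, 29% | 44, 49% | 70, 76% |

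Less dispersed tallies or other contrasts remove or reverse the gain:

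| Setting | plan | log scale |
|---|---|---|
| 10 v 10, shape 4, 2 v 6 | 96.6% | 96.9% |
| 10 v 10, shape 4, 2 v 4 | 66.9% | 66.8% |
| 14 v 6, smaller group more active, shape 8, 0.5 v 1 | 43.5% | 40.1% |
| 14 v 6, larger group more active, shape 2, 10 v 15 | 15.9% | 14.0% |
| 14 v 6, larger group more active, Poisson, 2 v 3 | 67.6% | 61.4% |

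**5. The test proposed below.** The figures in step 4 are for a parametric log-scale test. With the p-value taken by permutation of the unequal-variance t statistic on log(1 + child mean), 20 children, size was 4.0 to 5.8%. Power rose by up to about 25 points under strong skew and was about unchanged at shape 4 with 10 v 10. It fell by up to about 7 points in some settings with Poisson tallies or the larger group more active. These simulations gave every child equal observation time, so they do not measure the benefit of scaling to coded minutes.

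**The case against.** The strongest reply is that the skew is assumed. The documents give no mean, SD, share of zeros or dispersion for any tally. The plan already switches to adjusted degrees of freedom when variances differ, and at child level its error rate is sound. The log scale is not uniformly better: treating 84 sessions as independent (42/42) with negative-binomial tallies, the raw test beats log(1 + tally) by 2 to 10 points. The choice among log, square root, rank and count models is partly preference, and mean log(1 + rate) is not a rate ratio.

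All of that stands against a stronger reading that a reader might infer, namely that the plan's raw-scale tests will miss real differences. The documents do not support it. The sign and size of the power change depend on unstated inputs, and if sessions are the units the main error runs the other way, towards false positives.

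It is equally tempting to say that sessions were certainly analysed as independent. The wording points that way but does not settle it.

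The reply does not answer the missing unit or the missing adjustment for coded time. Both are gaps whatever the dispersion.

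**Conclusion.** The point holds in conditional form and is worth acting on, with medium confidence.

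- **Sessions as units:** false differences are likely, at 10 to 37% against a nominal 5%. This assumes 20 children split 10 v 10 and child log-SD 0.3 to 0.8.
- **Child means as units:** the test is valid. Any loss is of efficiency only and arises under strong right skew. For a three-fold difference and 14 v 6 children with the smaller group more active, it is 7 to 15 points (8 v 15%, 22 v 36%, 49 v 64%). For near-Poisson tallies it is nil or negative.

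Most of the value lies in fixing one time-scaled value per child; the log scale is a secondary gain. The point covers 3-AAT frequency. The skew argument does not carry over to the 0 to 36 bond score or the modal intensity code.

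**What to change.** For 3-AAT frequency only, replace the t-test wording in the Design section and the Statistical Analysis Plan with the following:

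1. State that the child is the unit of analysis and give the number of children in each verbal group. A re-enrolled child counts once.
2. For each child, compute the tally per 30 coded minutes in each coded session and average over that child's coded sessions.
3. Compare log(1 + rate) between verbal groups with the unequal-variance t statistic, and take the p-value by permuting the verbal label across children.
4. Report raw group mean rates alongside.

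The cost is one paragraph and a short script, provided the coded minutes per session are on file. Because the plan is written after the sessions were coded, label the result as a revised analysis. The downsides are that the tested difference is on a log scale, and that a few points of power (up to about 7 in the settings tried) may be lost if tallies are near Poisson or the larger group is the more active one.
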